#### **4.3. Statistical Methods for Aim 2:**

This aim focuses on the evaluation of multiple clinical outcomes of local relevance and interest, all widely used in HF outcomes research. SCHFI (v.6) assesses three self-care domains- Maintenance, Management, and Confidence-using Likert scales.(34) Each domain is scored independently and standardized to a score of 100. The recommended time interval between administration is 3 months or less. Our primary outcome is specifically change in the Management scale, as this addresses the behaviors most closely tied to our intervention: active patient decision-making to identify symptoms and take actions to minimize them. EQ-5D assesses five domains – Mobility, Self-care, Usual activities, pain/discomfort, and anxiety/depression- using Likert scales and overall health using a visual analog scale. 6MWT and LVEF are measured in meters and percentage, respectively. Frequency of acute care visits will be abstracted from UHI clinical records and recorded as number of unscheduled visits in six months. Drs. [name] and [name] will co-lead this Aim.

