## 2. AIMS

Self-care is an important, yet underutilized, intervention in the management of chronic conditions, especially for low-resource settings because it shifts fundamental care tasks from providers to patients while empowering patients and enhancing quality of life. In this project, we will study the implementation and preliminary clinical effectiveness of Medly Uganda, a patient-facing mobile health application designed to improve self-care among patients within heart failure. The multi-level engagement of stakeholders and the grounding in user-centered design principles will serve to enhance the feasibility and scalability of Medly Uganda.

**AIM 1:** Assess the implementation of Medly Uganda at the Uganda Heart Institute in Kampala, Uganda. We will use mixed methods to assess feasibility, acceptability, and adoption of the app and accompanying provider dashboard. Sources of data will include surveys and interviews with patient and clinician participants and app and dashboard usage data.

**AIM 2:** Assess the preliminary effectiveness of Medly Uganda on clinical outcomes. Our primary outcome is improvement in the Self-Care in Heart Failure Index, a widely used, evidencebased instrument which we will evaluate at 0,3, and 6 months. We will also assess changes in HRQoL using the brief EQ-5D tool as well as the 6-Minute Walk Test, left ventricular ejection fraction, and frequency of acute care visits at the same time points.

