## 3. STUDY PROTOCOL

### 3.1. Study Setting

Uganda is a low-income country in East Africa with a population of 35 million and a rising burden of NCD. Resource allocation toward NCD has been poor and the capacity of public sector healthcare facilities to

address NCD, including HF, is low. The proposed project will be conducted at UHI, the highest level referral center for cardiac care in the country and the only public sector facility with robust HF services. UHI is located on the campus of Mulago National Referral Hospital in the capital city, Kampala. Its outpatient clinic serves 70-100 adult patients per day from throughout Uganda and neighboring countries and from across socioeconomic and demographic spectra. Clinical care is provided by 12 physicians, 6 fellows, and 18 nurses. The coordinating center for this project is the Uganda Initiative for Integrated Management of Non-Communicable Disease (UINCD), a research consortium co-directed by the co-Principal Investigators (PI) UINCD headquarters are located on Mulago campus, thereby allowing for ease of communication and collaboration between the clinical research site and the coordinating center.

In Uganda, in 2016, there were 22 million active mobile phone accounts and 340,000 land-lines, a ratio similar to other LMIC where mobile telephony became ubiquitous while circumventing land-line infrastructure. Cellular signals of the three main carriers are strong throughout the country. Given these features, Uganda has seen numerous mHealth pilot studies, many of which failed to progress beyond pilot stage due to lack of contextually appropriate design and testing and lack of engagement with key stakeholders. In response to this so-called “pilotitis”, all mHealth projects are now required to exhibit genuine local ownership/co-ownership and collaboration with relevant government entities, which we demonstrate in the current proposal.

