### 3.2. Study Design

This is a single-center prospective cohort study conducted at UHI. The study period is 6 months. Patient participants will have three study timepoints (Baseline, Month 3, and Month 6) while data will be collected from clinician participants only at Month 6.

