### 3.4. Intervention

Participants will be asked to initiate a USSD session by dialing the Medly Uganda sub-code and entering a unique PIN every Monday, Wednesday, and Friday morning for six months and whenever they experience concerning symptoms. If a participant has not done so by 11AM on the designated days, RapidPro will generate an SMS reminder. Each interactive USSD session will present a series of symptom-based questions to the participant and be followed by a tailored SMS message. While USSD session content will not remain on the participant's phone, SMS' will. This allows participants to retain and review messages, thereby reinforcing educational content. There are four Status categories: Stable, Fluid Overload, Urgent, and Critical. If Stable, participants will be sent one of six encouraging and educational messages. If Fluid Overload, Urgent or Critical, patient participants will be sent a message that identifies the symptom and recommends an action and the on-duty nurse will be sent an accompanying alert. Urgent and Critical alerts will also be sent to the on-duty doctor (Algorithm- attached to HIC application). The nurse is expected to call the patient for Urgent and Critical alerts within 60 and 15 minutes, respectively. Nurse phone call interactions will be guided by a standard operating manual. One UHI nurse and one

UHI doctor will be designated rotating 'on-duty' responsibility to monitor clinician alerts and the dashboard seven days a week. The doctor will be available to provide clinical supervision to the nurse as needed and they will have a daily in-person or by-phone huddle around 4PM to review the prior 24 hours system activity. Drs.[name] or [name] will be available at all times to provide an additional layer of technical and clinical backup to the designated clinicians as needed.

[figure not shown]

Figure 3. Technical design of Medly Uganda including the integration of the patient-facing application and the clinician dashboard.

Clinicians will access the dashboard by smartphone or computer using a unique username and password and entering the patient participant's phone number. The dashboard then presents a screen that includes basic demographic information, baseline clinical information from study entry. The screen also includes a color-coded matrix that graphically displays how the patient answered each question and the assigned Status from the current

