### 3.4. Inclusion/Exclusion Criteria:

We will use consecutive sampling to identify potential patient participants. Based on UHI patient volume and demographics, we anticipate an equal distribution of urban- and rural-dwellers and 60:40 female:male ratio. For the clinician sample, we will seek to enroll all clinicians who meet inclusion/exclusion criteria (n=5 nurses; 5 doctors).

Patient inclusion criteria include: 1. UHI patient presenting for routine or urgent outpatient visit; 2. Currently living in Uganda and not planning to travel abroad for six months; 3. Age  $\geq 18$  years; 4. Symptomatic (New York Heart Association Class II, III, or IV) HF regardless of LVEF; 5. Access to a mobile phone; 6. Basic reading skills in English, Luganda, and/or Runyankole.

Patient exclusion criteria include: 1. Life expectancy  $<$  six months; 2. Active medical condition requiring hospitalization, such as cardiac ischemia (acute electrocardiographic changes and/or positive biomarkers, if available), syncope, or significant fluid overload; 3. Pregnancy; 4. Inability to provide informed consent.

Clinician inclusion criteria include: 1. UHI staff doctor or nurse; 2. Anticipated assignment to Medly Uganda duties at least once during the study period.

Clinician exclusion criteria includes unwillingness to provide informed consent.

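### Acute care visits are counted from UHI records alone, so visits elsewhere are missed and a comparison over time may be biased in a direction the documents do not settle

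*Combined protocol and SAP*

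**What the plan says.** Section 2 (Aims) lists acute care visits among the Aim 2 clinical outcomes, to be assessed as "frequency of acute care visits at the same time points", meaning 0, 3 and 6 months. Section 4.3 (Statistical Methods for Aim 2) names one source and one window: "Frequency of acute care visits will be abstracted from UHI clinical records and recorded as number of unscheduled visits in six months".

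Other sections describe who is counted and how the intervention works:

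- Section 3.1 (Study Setting), on UHI: "Its outpatient clinic serves 70-100 adult patients per day from throughout Uganda and neighboring countries".
- Section 3.4 (Inclusion/Exclusion Criteria) sets no distance limit. The residence rule is "Currently living in Uganda and not planning to travel abroad for six months". On the expected mix: "we anticipate an equal distribution of urban- and rural-dwellers".
- Section 3.4 (Intervention), for any status other than Stable: "patient participants will be sent a message that identifies the symptom and recommends an action". The on-duty nurse is also alerted. In addition, "The nurse is expected to call the patient for Urgent and Critical alerts within 60 and 15 minutes, respectively".
- Section 3.2 (Study Design): "This is a single-center prospective cohort study conducted at UHI". No comparison group is described.

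The Baseline, Month 3 and Month 6 procedures in section 3.4 (Procedures) include no question about care at other facilities and no request for outside records. Section 4.3 (Potential Challenges and Alternative Approaches) does not mention missed visits.

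**The concern.** The outcome is named as acute care visits, but what will be measured is unscheduled visits to one referral center in Kampala. A participant who worsens and is treated only at a district facility contributes zero.

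Two problems follow, and they differ in strength. The first is undercounting, which comes directly from the plan as written. The second is conditional. The intervention gives patients a direct line to staff at the one facility whose visits are counted, so it could change where they seek care as well as how often they need it. Without a control arm, nothing in the data would reveal such a change. A change in the UHI count could then be read as a change in acute care when part or all of it is a change of place.

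**Working it through.** The plan gives no expected visit rate, UHI share or power statement for this outcome, so there is no planned figure to reproduce. The sample size in section 4.1 concerns the SCHFI only.

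**Inputs from the documents:** UHI records as sole source and a single six-month count (section 4.3, Aim 2); an equal urban and rural split (section 3.4, Inclusion/Exclusion Criteria); no control arm (section 3.2).

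**Assumed inputs, because the documents give none:** the share of acute visits that occur at UHI, and a true rate ratio of 0.80 (a 20% fall) for illustration.

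**Step 1: undercounting.** Assume equal visit rates in urban and rural patients, 90% capture at UHI for urban patients and 10% to 70% for rural patients. Captured share = 0.5 x urban share + 0.5 x rural share.

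- Rural 10%: 0.5 x 0.90 + 0.5 x 0.10 = 0.50, so 50% of visits are missed.
- Rural 70%: 0.5 x 0.90 + 0.5 x 0.70 = 0.80, so 20% are missed.

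**Step 2: comparison over time.** Observed ratio = true ratio x (UHI share with the app / UHI share in the comparison period).

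| UHI share, before to with app | Calculation | Observed ratio |
|---|---|---|
| 50% to 50% | 0.80 x 0.50/0.50 | 0.80 (unbiased) |
| 50% to 60% | 0.80 x 0.60/0.50 | 0.96 |
| 50% to 70% | 0.80 x 0.70/0.50 | 1.12 |
| 30% to 50% | 0.80 x 0.50/0.30 | 1.33 |
| 70% to 80% | 0.80 x 0.80/0.70 | 0.91 |
| 50% to 40% | 0.80 x 0.40/0.50 | 0.64 |

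**Step 3: break-even.** A true ratio of 0.80 shows as no change when the share rises by a factor of 1/0.80 = 1.25, for example from 50% to 0.50 x 1.25 = 62.5%. A smaller rise understates the fall but keeps its direction. A larger rise reverses it. Any drop in the share exaggerates the fall.

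**Step 4: which way the share would move.** Section 3.4 (Intervention) establishes contact with UHI staff. It does not say whether the message or the call directs patients to UHI or to a nearer facility. That would depend on the algorithm, which is attached to a separate ethics application, and on the nurses' operating manual. Neither is reproduced in the protocol text.

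**Step 5: the comparison period.** The Aims promise assessment at 0, 3 and 6 months, but section 4.3 defines one six-month count with no pre-enrolment window. The baseline value that Step 2 needs is therefore undefined.

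**The case against.** The best defense is that UHI is where these patients go. Section 3.1 describes it as the one public facility with well-developed heart failure services and calls public capacity elsewhere low. Participants are recruited from people already attending UHI, including for urgent visits. No section states that a rural patient who worsens goes to a nearer facility first. This stands as a reason why the loss may be modest. It does not show that distant patients reach UHI for every acute episode, and the plan has no means of checking.

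A second defense is that a stable undercount cancels in a ratio. This is correct, and it limits the point. Bias in a comparison over time needs a change in UHI's share, not merely an incomplete share.

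A reader might go further and infer that the app will draw visits to UHI, so that the outcome will move the wrong way or can show nothing about acute care. The documents do not support that. They do not say that alerts steer patients to UHI, a modest rise in share keeps the right direction, and a falling share would flatter the app.

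Finally, this is one of several non-primary measures in an aim described as preliminary. The primary outcome, change in SCHFI Management, is unaffected.

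**Conclusion.** The point holds in two parts. First, the plan as written undercounts acute care visits, because it takes them from one facility for participants who may live anywhere in the country. Second, a comparison over time is open to bias if UHI's share of visits changes. The direction cannot be settled from the documents: a true ratio of 0.80 could show as 1.12 (50% to 70%), as 0.64 (50% to 40%), or correctly as 0.80 (constant share).

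All shares are assumptions. The 20% to 50% missed in Step 1 is likewise a scenario and not an estimate for this cohort. Text between sections 3.2 and 3.4 was not available for this check, so a provision there cannot be excluded. The sections that define the procedures and the outcome contain none. The change is worth making, but the primary analysis does not depend on it.

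**What to change.** 1. At the existing Month 3 and Month 6 visits, add a Qualtrics item on the number and place of unscheduled visits and admissions at any facility since the last visit.
2. Ask the same at Baseline for a stated prior period, equal in length to the follow-up period with which it will be compared. This also supplies the missing time-0 value.
3. Keep UHI record abstraction for all participants, including those who drop out. The new item should supplement the records, because self-report is lost with dropout and section 4.1 allows for 25% loss.
4. Report UHI and non-UHI visits separately, and label any UHI-only count *unscheduled UHI visits*.

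If any-facility visits are recorded in the same way in both periods, the capture ratio in Step 2 is 1 and a true 0.80 shows as 0.80.

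**Cost.** A short item (number, place, visit or admission) on forms already completed by existing staff. The report should state three downsides: recall error; missing self-report for dropouts, who may include patients who worsened; and a Baseline count that may be raised by the index episode in patients enrolled at an urgent visit. The last could produce a fall through regression to the mean in an uncontrolled cohort.

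Flagging visits that follow a nurse call should not be relied on to isolate app-prompted visits. A Fluid Overload status also sends an action message, while calls are expected only for Urgent and Critical alerts, so visits prompted by SMS alone would be misclassified.

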#### **4.3. Potential Challenges and Alternative Approaches:**

First, participant dropout may occur due comprehension or technical challenges using the app, accessing a stable mobile network, or loss of interest. We will conduct interim analyses of follow-up rates and data completeness and adjust enrollment upward if needed. UHI has a sufficiently large eligible patient population to allow for this. Second, it is plausible that the need to enter a PIN could dissuade app use. If this is a consistent concern in Month 3 RN reviews, we will consider removing it after consultation with partners. Third, technical challenges may arise with the app or dashboard. A UHI Information Technology Specialist, already identified, will work with GoodCitizen to address such issues. Fourth, the frequency of alerts and calls could promote clinician burnout. [name] will monitor this through monthly check-ins with staff. UHI has sufficient staff to allow us to increase the number of clinician participants should this occur.

